16.1 Expedited Reporting

- The Principal Investigator must be notified within 24 hours of learning of any serious adverse events, regardless of attribution, occurring during the study.
- The Northwestern University IRB must be notified within 10 business days of “any unanticipated problems involving risk to subjects or others” (UPIRSO).
NU IRB considers UPIRSOs to include any incident, experience, or outcome that meets all of the following criteria:
 - (1) Unexpected (in terms of nature, severity, or frequency) given (a) the research procedures that are described in the protocol-related documents, such as the IRB-approved research protocol and informed consent document; and (b) the characteristics of the subject population being studied;
 - (2) Related or possibly related to participation in the research (in this guidance document, possibly related means there is a reasonable possibility that the incident, experience, or outcome may have been caused by the procedures involved in the research); and
 - (3) Suggests that the research places subjects or others at a different or greater risk of harm (including physical, psychological, economic, or social harm) than was previously known or recognized.
- Only unanticipated problems involving risk to subjects or others (UPIRSOs) will be promptly reported to the HRPO.
- The FDA will be notified within 7 business days of any unexpected fatal or life-threatening adverse event with possible relationship to study drug, and 15 business days of any event that is considered: 1) serious, 2) unexpected, and 3) at least possibly related to study participation.

## Overview

This is a 2-year, randomized, double-blind placebo-controlled study of zoledronic acid to evaluate its efficacy and safety for the prevention of bone loss and maintenance of bone strength in individuals with recent onset SCI (see protocol). Subjects were randomized at the baseline visit to receive either zoledronic acid or placebo. At the end of the first year of the study, each treatment group was re-randomized to either zoledronic acid or placebo to evaluate the durability of response to zoledronic acid and the utility of serum bone markers to guide therapeutic decision making. DXA imaging, CT imaging of knee and bone markers were obtained at baseline, 3 months, 6 months, 12 months, 18 months and 24 months. CT imaging of the hip was obtained at baseline, 6 months, 12 months, and 24 months.

## Study Objectives/Statistical Hypotheses

**Hypothesis 1a.** In participants treated shortly after acute SCI with a single infusion of zoledronic acid, the mean loss of bone after one year at skeletal sites in the lower extremity will be less than that determined for participants who received placebo. Hip areal bone mass density (aBMD) will be assessed as the primary endpoint.

**Hypothesis 1b:** In participants treated shortly after acute SCI with a single infusion of zoledronic acid (zol/placebo) as well as those receiving a second treatment with zoledronic acid (zol/zol), the mean loss of bone after two years at skeletal sites in the lower extremity will be less than that determined for participants who received placebo for two years (placebo/placebo).

**Hypothesis 1c:** The effects of a single infusion of zoledronic acid after acute SCI will wane over time; retreatment with zoledronic acid after one year will result in greater maintenance of bone than a single infusion with zoledronic acid.

**Hypothesis 1d:** Initiation of treatment with zoledronic acid at one year after acute SCI in people not previously treated (placebo/zol) will still result in preventing further bone loss compared to no active bone-specific treatment (placebo/placebo); loss of bone mass that has occurred during the initial year without treatment will not be reversed, however.

## Endpoints

**Primary endpoints.** The primary endpoints in this study are the percent-change in aBMD, evaluated by DXA, in the non-dominant (1) total hip and (2) femoral neck skeletal sites. If data on the non-dominant hip are unavailable, we will use aBMD for the dominant hip. Percent-change will be calculated as  $((\text{aBMD}_{\text{follow-up}} - \text{aBMD}_{\text{baseline}}) / \text{aBMD}_{\text{baseline}}) \times 100\%$ .

**Key secondary endpoints.** Secondary endpoints include: (1) integral volumetric bone mineral content (Int.vBMC) distal femoral epiphysis, (2) Int. vBMC tibial epiphysis, and (3) Int.vBMC distal femoral metaphysis measured by QCT. Percent-change will again be calculated for each outcome.

**Additional secondary endpoints.** CT biomarkers: Trabecular volumetric bone mineral density (Tb.vBMD; g/cm^3) and cortical volumetric bone mineral content (Ct.vBMC; g) and bone volume (Ct.vBV; cm^3) at epiphyseal and metaphyseal regions. For the diaphyseal region, Ct.vBMC and Ct.vBV. WISCI.

**Exploratory endpoints.** Torsional strength index (TSI; cm^3) for each skeletal region. Stiffness and strength at the hip, distal femur, and proximal tibia determined by CT-based finite element analysis. Serum markers of bone metabolism: P1NP, BSAP (bone formation markers), and CTX (bone resorption marker).

## Statistical Methods

### *Diagnostics*

All variables will be plotted to examine distribution shapes as well as percentage of missing values. The mixed modelling proposed below uses both all available observations without deleting cases and imputed data. Residuals will be examined for each model fitted in case of unexpected violations of assumptions. Analysis will be performed as ITT (intention to treat): patients will be analyzed according to the treatment arm to which they were randomized.

## ***Missing Data***

Missing data will primarily be inputted by maximum likelihood estimation using a mixed effects model. A sensitivity analysis will be done latter, by using a multiple imputation methodology before modelling. Here, imputation of missing data will be based on sampling from a normal distribution using a mean value of the subjects' last observed value and standard deviation (over treatment groups) of the observed data at the missing endpoint (3, 6, or 12 months). This is a multiple imputation version of Last Observation Carried Forward (LOCF) single imputation method. Note, a subject's last observation may be the Baseline observation. One hundred imputed datasets will be used in this analysis. The linear mixed-effects model described below will be used for each imputation dataset, and the overall results will be calculated to take account of the variability both within and between imputation datasets using standard methods (Little & Rubin, 2002).

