1.1. Rationale

Spinal cord injury results in acute bone loss which is rapid and profound.

Spinal cord injury (SCI) results in marked acute loss of bone, primarily limited to those bony structures that are below the level of the neurologic lesion and non-weight-bearing, with little or no loss of bone at the spine and in bony structures that are supraspinal.^{1,2} The bone loss occurs rapidly, with the greatest decrease in bone density observed during the first 6-18 months after spinal cord injury, and is profound in magnitude, commonly being in the range of 15-30% at the hip, and potentially even higher at sites of less weight-bearing and of greater trabecular content below the hip.^{1,2} The degree of bone loss has been shown to be highly dependent on the degree of loading, with individuals having incomplete motor lesions and capable of some degree of weight-bearing having less bone loss than those with motor complete lesions.³ Lower extremity bone loss is similar in paraplegics and quadriplegics with similar motor function loss; upper extremity bone mass is unaffected in paraplegics but variably affected in quadriplegics, dependent on the degree of impairment of upper extremity function⁴. Age, weight and gender are important determinants of bone loss.³ Initially, bone mineral density (BMD) decline is reported to be most marked in areas rich in trabecular bone, with relative sparing of cortical bone ^{2,5-8} though recent studies from our group indicate significant acute loss of cortical bone as well ⁹ This enhanced rate of bone loss can be observed for between 2 and 5 years after acute SCI, at which time a new steady state is reached and bone resorption and bone formation become once again tightly coupled, but now at a new “set point” with bone mass that is 30-50% below the level prior to the injury.^{2,5-7} After this point in time, there is a much reduced rate of bone loss, with other secondary causes of bone loss, e.g., estrogen withdrawal, endocrinopathies, being potentially important contributors to further changes in bone status.

Loss of bone mass after acute SCI is paralleled by a marked decrease in bone strength.

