Subjects will all be in-patients or recently discharged from RIC/SRALab. Patients are not transferred to RIC/SRALab unless medically stable, but as the acute phase of their illness may have associated complications as well as requiring psychological adjustment; patients will be approached for inclusion into this study when deemed appropriate by their attending psychiatrist and/or nurse practitioner. If patients express an interest in the study, the study procedures will be explained, their questions answered, and the informed consent process as described in the preceding section will take place. Their medical record will be reviewed to assure they meet all inclusion and exclusion criteria. Assessments performed exclusively to determine eligibility for this study will be done only after obtaining informed consent. Assessments performed for clinical indications (not exclusively to determine study eligibility) may be used for baseline values even if the studies were done before informed consent was obtained.

There will be 10 visits for this study: Screening, Baseline, and 8 follow up visit at 3, 6, 9, 12, 15, 18, 21, and 24 months after baseline. It is desirable but not required for research subjects attend visits at 3, 9, 15, and 21 months after baseline. It is understood that based on where research subjects live and available transportation, visits every 3 months may not be possible. If a research subject cannot attend the follow-up visits at 3, 9, 15, or 21 months, the visit will be conducted over the phone and study supplements will be mailed to the research subject.

All patients will have their 25-hydroxyvitamin D levels measured at the screening visit if a recent test has not been done within the past 3 months. Those patients whose levels are lower than 20 ng/ml and are currently not on vitamin D will be dispensed a 7 day supply of vitamin D 50,000 IU. Infusion of study drug at baseline will only take place after a repeat 25-hydroxyvitamin D serum level meeting the study criteria will have been documented. Those patients whose levels are lower than 20 ng/ml but greater than or equal to 15 ng/ml and are currently on at least vitamin D 1,000 IU daily will be eligible for the study and will not need a repeat 25-hydroxyvitamin D serum level prior to infusion.

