## ***Secondary analyses***

Secondary analysis will be divided into three main sections:

- a) Effect of functional capacity (WISCI) on aBMD of total hip and femoral neck percent-change; A secondary interaction analysis will be performed for the primary endpoint, exploring the effect of WISCI. The interaction of treatment with WISCI score will be fitted as a fixed effect (in addition to the WISCI score itself), with the resulting estimated treatment differences being shown for continuous scores of the WISCI scale.
- b) Secondary endpoint analysis at 12 months;

The primary analysis described above will be applied for all the three key secondary endpoints at 6, and 12 months visits, with the fixed sequence order described above. Appropriate p-values adjustments to compensate for a possible increased risk in Type I errors due to multiple secondary outcomes measurements will be done using a stepwise Dunnett procedure. All reporting will include both adjusted p values and raw effect sizes.

c) Primary and secondary endpoint analysis at 24 months.

Primary endpoint (total hip and femoral neck aBMD, measured by DXA) and secondary endpoints will be analyzed at 24 months. Here, we will study 4 groups of patients: 24 months of treatment, 24 months of no-treatment, switch from treatment to placebo at 12 months, switch from placebo to treatment at 12 months. A linear mixed model with the four groups, controlling for Baseline aBMD at the hip and ambulatory status measured by WISCI will be fitted to predict percent-change from baseline for each endpoint.

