### ***Sensitivity analyses***

This analysis will assess the robustness of the efficacy conclusions regarding the choice of maximum likelihood estimation as the primary method for accounting for missing data. The primary mixed effects model described above will be repeated after multiple imputation, as described above.

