## Analysis Plan Summary

Endpoint	Statistical Method	Model/Covariates	Missing Data	Objective
% Change from Baseline at 6,12 months with total hip and femoral neck aBMD, DXA	MEM	Baseline total hip/ femoral neck aBMD, visit, WISCI score; (subjects as random effects)	MLE	Primary Analysis
% Change from Baseline at 6,12 months with total hip aBMD, DXA	MEM	Baseline total hip aBMD, visit, WISCI score; (subjects as random effects)	Multiple Imputation	Sensitivity Analysis
% Change from Baseline at 6,12 months with total hip aBMD, DXA (a)	MEM	Baseline total hip aBMD, visit, WISCI score, (subjects as random effects)	MLE	Secondary, Interaction Analysis
% Change from Baseline at 6, 12 months with femoral neck aBMD, DXA (b)	MEM	Baseline total hip aBMD, visit, WISCI score; (subjects as random effects)	MLE	Secondary Analysis
% Change from Baseline at 6,12, months with QCT Int.vBMC Femoral Epiphysis (b)	MEM	Baseline total hip aBMD, visit, WISCI score; (subjects as random effects)	MLE	Secondary Analysis
% Change from Baseline at 6,12, QCT Int.vBMC Femoral Metaphysis (b)	MEM	Baseline total hip aBMD, visit, WISCI score; (subjects as random effects)	MLE	Secondary Analysis
% Change from Baseline at 24 months with total hip aBMD, DXA (c)	MEM	Baseline total hip aBMD, visit, WISCI score; (subjects as random effects)	MLE	Secondary Analysis
% Change from Baseline at 24 months with	MEM	Baseline total hip aBMD, visit, WISCI	MLE	Secondary Analysis

femoral neck aBMD, DXA (c)		score; (subjects as random effects)		
% Change from Baseline at 24 months with QCT Int.vBMC Femoral Epiphysis (c)	MEM	Baseline total hip aBMD, visit, WISCI score; (subjects as random effects)	MLE	Secondary Analysis
% Change from Baseline at 24 months with QCT Int.vBMC Femoral Methaphysis (c)	MEM	Baseline total hip BMD, visit, WISCI score; (subjects as random effects)	MLE	Secondary Analysis

(a) Secondary analysis phase 1: Interaction Analysis for primary endpoint with WISCI; (b) Secondary analysis phase 2: Secondary endpoints at 12 months; (c) Secondary analysis phase 3: Primary and Secondary endpoints at 24 months. aBMD (areal bone mineral density); MEM (mixed effects model); MLE (maximum likelihood estimates); WISCI (walking index for spinal cord injury).

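### The only missing-data sensitivity analysis overstates its own standard error and assumes that bone loss stops at the last visit, so its disagreement with the primary result may be an artefact

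*SAP*

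**What the plan says.** The primary analysis handles missing values by maximum likelihood in a mixed model (SAP, Missing Data). One sensitivity analysis is added, and the SAP relies on it to show that the efficacy conclusions are robust: "The primary mixed effects model described above will be repeated after multiple imputation, as described above" (SAP, Sensitivity analyses).

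The imputation rule draws from a normal distribution whose mean and SD are the patient's "last observed value and standard deviation (over treatment groups) of the observed data at the missing endpoint (3, 6, or 12 months"). The SAP describes its nature itself: "This is a multiple imputation version of Last Observation Carried Forward (LOCF) single imputation method". It adds that a patient's "last observation may be the Baseline observation", which is 0% change. One hundred datasets are combined by the standard within-plus-between rule. Nothing conditions on arm, time trend or earlier visits. The SAP does not say whether aBMD or percent change is imputed, or whether the SD is taken within or across arms.

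Two gaps in scope follow.
- The sensitivity row of the Analysis Plan Summary covers only "Change from Baseline at 6,12 months with total hip aBMD, DXA", although the primary model it repeats covers total hip and femoral neck.
- The rule names months 3, 6 and 12. The SAP also states that "Primary endpoint (total hip and femoral neck aBMD, measured by DXA) and secondary endpoints will be analyzed at 24 months", and gives no rule for that visit.

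Protocol 14.1 also describes LOCF, but says that the SAP supersedes it.

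**The concern.** A robustness check needs a plausible assumption about the missing values and a standard error that matches the estimator. This rule has neither.

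**Spread.** The carried-forward value already contains the patient's deviation from the mean. Adding the full marginal SD of the visit counts that variation again. This holds whether or not bone loss continues.

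**Centre.** Carrying the last value forward assumes that loss stops there. Protocol 1.1 places "the greatest decrease in bone density observed during the first 6-18 months after spinal cord injury", so in this population loss is expected to continue between month 6 and month 12.

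At stake is the reading of the check. If it disagrees with the primary result, the SAP gives no way to tell a real sensitivity to missing data from a product of the rule.

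**Working it through.** **Inputs.** Protocol 14.3: 30 per arm; dropout expected below 20%; Table 2 left total hip -3.40 (SD 3.51) on zoledronic acid and -13.83 (SD 2.01) on placebo, difference 10.43; right total hip -2.80 and -18.21 (placebo SD 2.39); planning SD 9.02 and difference 6.5. SAP: alpha 0.05 (two-sided assumed), 100 imputations.

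**Assumptions not in the documents.** Percent change is imputed; month-6 loss is f = 0.7 of month-12 loss (0.5 to 1.0 tried); the SD is equal at months 6 and 12, with correlation 0.8. Error rates and power come from simulation of the month-12 two-sample comparison with standard combining rules.

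**Plan's own figure.** 6.5 / (9.02 × √(2/30)) = 6.5/2.329 = 2.79, which gives 79.7% power (normal) or 78.4% (t). The stated 80% is reproduced.

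**Standard error.** Let m of n be missing per arm and s be the imputation SD. Over 100 draws the added noise averages out of the estimate. It adds about m·s²/n² to the within variance and 1.01·m·s²/n² to the between variance, so the excess per arm is 2.01·m·s²/n². For the left hip with m = 6:
- True variance: (3.51² + 2.01²)/30 = 0.545, spread 0.74.
- s² within arms: (12.32 + 4.04)/2 = 8.18. Excess over two arms: 2 × 2.01 × 6 × 8.18/900 = 0.219.
- s² ignoring arm: 8.18 + (10.43/2)² = 35.38. Excess: 0.948.
- No loss after month 6: √(0.545 + 0.219) = 0.87, or √(0.545 + 0.948) = 1.22.
- With f = 0.7, mixing two means within an arm adds 0.2 × 0.8 × 0.3² × (13.83² + 3.40²)/30 = 0.097. The SE becomes √0.861 = 0.93, or √1.590 = 1.26.

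Simulation gives 0.93 to 1.27 against 0.72 to 0.74. In the extreme where every missing patient has baseline as last value, it gives up to 1.59 against 0.65. If aBMD is imputed, with an assumed between-patient CV of 13%, the SE is about 2.4 against 0.8.

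**Bias.** Estimate = D + k(qA·LA − qP·LP), where D is the true difference, q the share missing, L the month-12 loss, and k = 1 − f (month 6 last) or 1 (baseline last).
- 20% per arm, k = 0.3: 10.43 − 0.3 × 0.2 × 10.43 = 9.80 (9.4 at f = 0.5; no bias at f = 1.0).
- 20% per arm, k = 1: 8.34. This needs every missing patient to have no follow-up scan at all.
- Overstatement needs qA/qP > LP/LA: 13.83/3.40 = 4.07 (left hip), 18.21/2.80 = 6.50 (right hip).

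**Power at the planned difference** (6.5, SD 9.02, 20% per arm, month 6 last): about 59%. Observed cases alone, 24 per arm, give 6.5 / (9.02 × √(2/24)) = 2.50, about 70% (normal).

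**No treatment effect.**
- Equal missingness: type I error about 0.00 to 0.02.
- 30% against 10% missing, both arms at placebo hip values, month 6 last: bias 0.3 × 0.2 × 13.83 = 0.83 or 0.3 × 0.2 × 18.21 = 1.09. Error is about 0.10 to 0.13 with SD 2.0 to 2.4, and 0.03 to 0.04 with SD 5 to 9.
- The same with baseline as last value for every missing patient and SD near 2: about 0.3.
- 20% against 10%: 0.00 to 0.04.
- aBMD scale: no inflation seen.

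These rates depend on the model. At 30% against 10%, a random-intercept fit that pools variance over visits gave 0.17 to 0.20 (month 6 last) and 0.56 to 0.60 (baseline only).

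**The case against.** A sensitivity analysis may deliberately depart from the primary assumption, and here the departure is mostly conservative. With similar missingness the difference shrinks and the SE is too large, so agreement with the primary result is credible. This stands. It does not excuse the standard error, which is too large under any assumption about the missing values.

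The pilot effect is also so large that nothing would change. Even the extreme case gives 8.34/1.59 = 5.2 standard errors. Under a proper imputation with 6 missing per arm, missing active-arm values would have to be about 29 points worse than predicted before left-hip significance is lost. This stands too, and it limits the harm.

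A reader might infer two stronger things that the documents do not support.
- **That the check has a type I error near 0.3.** In the month-12 comparison this needs no effect, 30% against 10% missing, an SD near 2 and baseline as last value for every missing patient. The protocol's only dropout experience is 3 of 60 at one year, and with 3 against 1 missing the error is 0.01 to 0.05.
- **That baseline will commonly be the last value.** Protocol section 7 says: "It is desirable but not required for research subjects attend visits at 3, 9, 15, and 21 months after baseline". That makes baseline plausible as the last value before month 6. At month 12 it would also require month 6 to be missed. Month 6 is not optional, and protocol section 8 offers travel help for it.

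The lack of a 24-month rule is a weaker point, because the SAP confines the sensitivity analysis to the primary model.

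**Conclusion.** The rule is wrong as written and should be replaced, but the primary analysis is not in danger. The excess standard error holds on every reading. For the left hip at 20% missing per arm it is roughly 1.25 to 1.75 times the true spread with month 6 as last value (0.93/0.74 = 1.26; 1.27/0.72 = 1.76), and more if aBMD is imputed. The bias depends on continued loss: about 0.6 points of 10.43 at the assumed f = 0.7, and none if loss stops at month 6. The usual result is over-conservatism. The rule can favour the arm with more missing data when the arms lose similar amounts of bone, so it does not guarantee the protection against overstated efficacy for which the superseded protocol text chose LOCF. The practical harm is that disagreement with the primary result may come from the rule alone. The sizes rest on the assumed scale, trajectory, correlation and dropout; the direction of the SE error does not.

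**What to change.** Replace the rule in the SAP's Missing Data section with multiple imputation of percent change by arm, conditional on baseline aBMD, earlier visits and WISCI, with parameters drawn and the residual SD used. In simulation at f = 0.7 (regression of month 12 on month 6 within arm) this gave a left-hip estimate of 10.4, an SE of 0.78 to 0.85 against a spread of 0.80, and a no-effect type I error of 0.035 to 0.053.

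This repeats the missing-at-random assumption of the primary model, so it adds little alone. Add a delta (tipping-point) range, fixed before unblinding and applied by arm.

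Run both for total hip and femoral neck, and correct the summary table to match. State whether values censored after the month-6 safety cut-off (protocol section 10, Excessive Bone Loss) are treated as missing. Extension to the 24-month analyses and a reference-based analysis are optional.

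The cost is SAP wording, standard software and a little more analysis work. No new data are needed.
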